3. OVERALL STUDY DESIGN

This is a multicentre, randomised, controlled, open-label, pragmatic, phase 2 basket study to assess the efficacy and safety of plitidepsin in different groups of immunocompromised patients with coronavirus disease 2019 (COVID-19) who require hospital care.

Approximately 150 patients are foreseen for the study, divided in 4 different groups of immunocompromised patients:

[figure not shown]
- **Group 1** –Patients receiving immune-suppression due to haematopoietic or organ transplantation.
- **Group 2** – Patients receiving B-cell depleting therapies.
- **Group 3** – Patients receiving other immune-suppressive therapies.
- **Group 4*** – Other situations with immune deficiencies.

*Not applicable in Spain

Whenever a patient can be allocated to more than 1 group, the priority will be group 1 > group 2 > group 3 > group 4*. In groups 1, 2, and 3, patients will be randomised to receive best standard

care (BSC) ± other antiviral (if clinically indicated) on control arm and BSC + plitidepsin on experimental arm. Group 4* will not be controlled, as shown in [Figure 9](#).

*Not applicable in Spain

*Not applicable in Spain

Figure 9 Algorithm for Patient Assignment in NEREIDA Basket Trial.

Stratification:

- Group 1: ISARIC mortality (<9/≥9) | Type of graft (allogeneic haematopoietic/lung or intestinal/other)
- Group 2: ISARIC mortality (<9/≥9) | Disease (haematological neoplasm/other)
- Group 3: ISARIC mortality (<9/≥9) | Disease (neoplasia/other)
- Group 4*: Not applicable

*Not applicable in Spain

Study periods:

The study will include a Screening period, a Treatment period and a Follow-up period.

The Screening period starts once the patient has provided written informed consent and ends when the patient is randomised in the study. Parameters assessed during this time will serve as the baseline values. The screening procedures should be preferably performed within 24 h prior to administration of study treatment, allowing a maximum of 48 h prior to administration of study treatment if required.

The Treatment period starts on Day 1 (date of randomisation) to 24 h after the last dose of the antiviral therapy; if no antiviral was given in the control arm, then the treatment period will finish on Day 4, for data management purposes. Antiviral treatment must always be started on the randomisation date.

The Follow-up period starts after the end-of-treatment and lasts until the end-of-study.

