5.2.3 Study Discontinuation

Study discontinuation occurs when an enrolled patient ceases to participate in the study, regardless of the reason. Patients will remain on study until patient consent withdrawal, death, or the date of study termination (clinical cutoff) established by the Sponsor. The date and reason for study discontinuation will be clearly documented in the medical records of the patient.

If the patient withdraws consent for disclosure of future information, the Sponsor may retain and continue to use any data collected before such a withdrawal of consent. Additionally, patients may request destruction of any samples taken and not tested, and the investigator must document this in the site study records. Refer to the Schedule of Assessments ([Appendix 13](#)) for data to be collected at the time of study discontinuation and follow-up and for any further evaluations that need to be completed.

Reasons for study discontinuation can include, but are not limited to:

- Investigator's decision;
- Patient refusal as reason for discontinuation.

5.2.4 Lost to follow up.

A patient will be considered lost to follow-up if he/she repeatedly fails to return for scheduled visits on Days 8 (± 1), 15 (± 1), 30 (± 2), and 60 (± 3), and is unable to be contacted by the study site.

The following actions must be taken if a patient fails to return to the clinic for a required study visit:

- The site must attempt to contact the patient and reschedule the missed visit as soon as possible, counsel the patient on the importance of maintaining the assigned visit schedule, and ascertain whether or not the patient wishes to and/or should continue in the study.
- In cases in which the patient is deemed lost to follow-up, the investigator or designee must make every effort to regain contact with the patient (where possible, 3 telephone calls and, if necessary, a certified letter to the patient's last known mailing address or local equivalent methods). These contact attempts should be documented in the patient's medical record.

Should the patient continue to be unreachable, he/she will be considered to have withdrawn from the study with a primary reason of lost to follow-up.

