Pregnancy test (if patient is a WOCBP)	A urine or serum pregnancy test will be performed for female patients of childbearing potential (i.e., female patients who are not postmenopausal or surgically sterile) at screening.
Eligibility assessment	Documented review of all Inclusion and Exclusion criteria.
ISARIC-4C mortality score	Appendix 4
Adverse events	AEs that occurred after signature of the informed consent form will be reported.

The patient will be a screening failure if not all inclusion criteria are met or if any exclusion criterion is met. A patient should only be treated if eligibility criteria are still met according to assessments performed closest to first drug administration.

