5.6 PATIENT RANDOMISATION

Patients will be sequentially allocated in their respective group, following the algorithm depicted in [Figure 9](#).

Central randomisation will be implemented. In groups 1-3, patients will be assigned to the experimental or the control arms at a 1:1 ratio. Stratification will be performed in the randomised groups. The ISARIC-4C mortality score will be used as a stratification factor in all groups (score <9/≥9). In addition, the type of graft (allogeneic haematopoietic/lung or intestinal/other) will be used for Group 1, whereas the underlying disease will be considered for Groups 2 and 3. For Group 2, the factor categories will be haematological neoplasm vs other disease; the respective categories for Group 3 will be neoplasia vs other. Stratification is not applicable in the non-randomised Group 4.

Day 1 is defined as the day of randomisation. Treatment must start within the same natural day.

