[¥]Antiviral treatment period in both arms will end 24 h after administration of the last dose of the antiviral therapy. If no antiviral was given in the control arm, then the treatment period will finish on Day 4.

[†]See [Section 7.2.1 Adverse Events of Special Interest \(AESIs\)](#).

For patients included in the study (all randomised patients) but never treated, only the applicable forms at baseline and off-study visit modules of the e-CRF should be completed but SAEs occurring during screening period need to be reported (using paper SAE forms).

All cases of treatment discontinuation must be documented (date and reason) in the electronic case report form (eCRF). A subject may stop the study treatment but desirably should continue follow-up to the end of study.

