8.2 ANALYSIS POPULATIONS

8.2.1 Full Analysis Set (FAS) Population

All randomised patients who have taken at least 1 dose of study treatment (plitidepsin or control) and have completed follow-up for survival until day 30 (± 2). Patients who die before the end of follow-up period will also be included in the FAS population. FAS population will be analysed according to their randomised treatment arm.

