8.5 SUMMARY OF ESTIMANDS AND STATISTICAL TESTS

The primary estimand corresponding to the primary endpoint is defined as:

Treatment: Participants will be randomised to receive plitidepsin versus control in each group.

Population: Participants as defined through the inclusion and exclusion criteria, who have been randomised to the trial and who have taken at least 1 dose of study treatment (plitidepsin or control).

Variable:

–1-month all-cause mortality rate (Day 30 since randomisation).

Intercurrent events:

–The participant's data are collected and included in the analysis without regard for treatment discontinuation (treatment-policy strategy).

–In the event of the participant initiating another non-protocol therapy, 1-month all-cause mortality rate will be evaluated regardless of initiation of new non-protocol therapy (treatment-policy strategy).

Population level summary: the posterior probability associated for the odds ratio of 1-month all-cause mortality rate from a Bayesian logistic regression for each group comparison.

Below a summary table where main/supportive analyses are described. P values except for the primary analysis have to be considered as exploratory and nominal values will be shown.

Endpoints	Analyses
Efficacy primary endpoint	
1-month all-cause mortality rate.	
 -Bayesian odds ratio (primary analysis by CHBM) -Bayesian odds ratio (Berry's Method) - Unstratified odds ratio (Univariate Logistic regression) - Stratified odds ratio (Multivariate Logistic regression)
Key secondary endpoint	
Time to confirmed negativisation in SARS-CoV-2 antigen test or RT-PCR Ct > 30.	
 -Kaplan-Meier (unstratified and stratified) -Cox regression (unstratified and stratified)
Efficacy secondary endpoints	
Time to sustained end of COVID-related hospital care from the time of randomisation. Sustained discharge is defined as no subsequent admission within 30 days of initial end of hospital care [up to day 60 (± 3)], related to either COVID-19 or COVID-19 therapy	
 -Kaplan-Meier (unstratified) -Cox regression (unstratified)
Time to sustained improvement (defined in Section 7.1.3) and resolution of selected COVID signs/symptoms (See Appendix 10 - COVID-19 signs/symptoms checklist).	
 -Kaplan-Meier (unstratified) -Cox regression (unstratified)

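### Day-30 survival is not assured for randomised patients who never start treatment, and the primary mortality analysis leaves them out

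*Protocol*

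**What the plan says.** The notes under the treatment-period table in Protocol 5.7 deal with patients who are randomised but receive no treatment: "For patients included in the study (all randomised patients) but never treated, only the applicable forms at baseline and off-study visit modules" of the e-CRF are to be completed. The same sentence adds paper reporting of SAEs from the screening period. It asks for no later contact.

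The analysis populations then drop these patients. The primary estimand (Protocol 8.5, repeated in SAP 11.6.1) covers participants "who have been randomised to the trial and who have taken at least 1 dose of study treatment". The FAS (Protocol 8.2.1, SAP 8.6.2.1) has the same dosing condition and also requires that patients "have completed follow-up for survival until day 30", with earlier deaths kept. SAP Table 3 (section 11.8) reports the primary endpoint as frequencies in the FAS only.

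Three further provisions bear on who ends up untreated:

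- Protocol 5.5.1: "A patient should only be treated if eligibility criteria are still met according to assessments performed closest to first drug administration". Critical illness is the first exclusion criterion in Protocol 4.2.
- Protocol 5.6, on the interval after randomisation: "Treatment must start within the same natural day".
- Protocol 3, where control is best standard care (BSC) with or without an antiviral: "if no antiviral was given in the control arm, then the treatment period will finish on Day 4, for data management purposes".

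**The concern.** The exclusion takes place after randomisation in an open-label trial, and its trigger can be clinical. A patient who becomes critically ill between randomisation and first dose no longer meets the criteria, should not be dosed, and so leaves the mortality analysis. A patient who leaves on learning the allocation is lost in the same way. The treatment-policy strategy in Protocol 8.5 does not help, because it only operates on patients who have already had a dose.

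If such losses differ between arms, the mortality comparison is no longer the randomised one. If vital status was not recorded, nobody can show afterwards whether it mattered. Early closure does not remove the problem. SAP 6.0 drops formal testing but still offers the descriptive tables as a basis for comparing the arms numerically, and in small arms one missing death is visible.

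**Working it through.** **Step 1. Does any other rule secure Day-30 status for an untreated patient?**

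| Provision | What it offers | Is Day-30 status assured? |
|---|---|---|
| Protocol 5.7 note | Baseline and off-study modules, screening-period SAEs | No |
| Protocol 5.2.3 | "Patients will remain on study until patient consent withdrawal, death, or the date of study termination" | Implies continued follow-up, but conflicts with the specific instruction in 5.7 |
| Protocol 5.9 | Survival status at Day 60 or at early termination | Only if the patient stays that long; early termination may precede Day 30 |
| Protocol 7.4.2 | SAEs collected from consent to Day 60 or death | May catch a death but cannot confirm survival; immediate reporting starts at first treatment, and the paper route covers screening and the time after off-study |
| Protocol 5.2.2 | At least 31 days of follow-up after withdrawal, whenever possible | Only after at least one plitidepsin dose |
| SAP 9.0 | Death imputed if information is lost before day 28 | Only for discontinuation of treatment because of adverse events |

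None of these closes the gap. In addition, Protocol 5.4 continues accrual until the FAS target is reached, so untreated patients are in effect topped up.

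**Step 2. Which arm would lose patients?** Two readings are open.

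- If BSC alone counts as control treatment, nearly every control stays in. Losses then fall on plitidepsin patients who deteriorate before the infusion.
- If a dose means a drug, controls given no antiviral fail the FAS, and losses fall on the control arm.

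No section defines a control dose, so the direction is undetermined.

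**Step 3. Size.** The plan gives no figure on this point, so there is nothing to reproduce. From Protocol 8.1: n = 20 per arm, control mortality p = 20%, target reduction 12.5 points. Assumptions, not in the documents: no drug effect, k = 1 or 2 patients excluded from one arm only, and mortality q = 50% among them.

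Observed mortality in the arm that loses patients = (n × p − k × q) / (n − k), where n × p = 20 × 0.20 = 4 expected deaths.

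- k = 1: (4 − 0.5) / 19 = 18.4%, a fall of 1.6 points; 1.6 / 12.5 = 13% of the target effect.
- k = 2: (4 − 1) / 18 = 16.7%, a fall of 3.3 points; 3.3 / 12.5 = 27% of the target effect.

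If plitidepsin loses the patients, it looks better by these amounts. If control loses them, plitidepsin looks worse by the same amounts.

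**Step 4. Sensitivity of the protocol's decision scale.** Protocol 8.4.1 set a 65% posterior probability of superiority as the cut-off for further development. SAP v3.0 no longer produces that analysis, so this only shows how much one death weighs. The calculation uses one group with no borrowing and two assumed priors: Beta(1,1) on each arm's rate, or N(0,1) on the log odds ratio with a vague control logit. Here the excluded patients are actual deaths, which is harsher than Step 3.

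| Deaths, plitidepsin vs control | Beta(1,1) | N(0,1) |
|---|---|---|
| 4/20 vs 4/20 (all randomised) | 0.50 | 0.50 |
| 3/19 vs 4/20 | 0.62 | 0.61 |
| 2/18 vs 4/20 | 0.75 | 0.72 |
| 4/20 vs 3/19 | 0.38 | 0.40 |
| 4/20 vs 2/18 | 0.25 | 0.28 |

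**The case against.** The case on the other side is substantial.

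- **Arm and timing.** The pre-dose check in Protocol 5.5.1 names no arm and sits with the screening rules. Control antivirals must also start on the randomisation date, and the gap between randomisation and dosing is within one day. Few patients may be affected.
- **Other capture routes.** Protocol 5.2.3, 5.9 and 7.4.2 are not limited to treated patients, and the off-study module may itself record a death. Neither that module nor Appendix 13 was available for this check.
- **Declared choice.** The treated-only set is stated openly, is consistent between FAS and estimand, and belongs to a trial described as exploratory.
- **Early closure.** Recruitment has ended, the Bayesian analysis is gone, and SAP 11.0 and 11.1 already plan CRF listings and a disposition display.

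Most of this stands, and it rules out three stronger conclusions that a reader might draw. The first is that the check removes the sickest patients mainly from the plitidepsin arm and so favours the drug. That is a plausible inference under one reading of a control dose, but the other reading points the opposite way. The second is that no survival outcome exists for these patients; the general rules may have captured some. The third is that an all-randomised analysis is impossible; hospital records may still supply the status.

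The central point survives. No provision requires a Day-30 status for these patients, the specific instruction in 5.7 runs against the general ones, and a disposition table does not give a Day-30 outcome.

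**Conclusion.** The concern holds as a gap in assured follow-up combined with a post-randomisation exclusion. It does not hold as a demonstrated bias in a known direction. The exclusion can depend on prognosis and can differ by arm. At the planned 20 per arm, one or two untreated patients would move one arm's mortality by 1.6 to 3.3 points under the assumptions in Step 3, towards or away from plitidepsin according to which arm loses them. The true size is unknown, because the documents give neither the number never treated nor their mortality. Since the 65% rule is no longer applied, the present consequence is a descriptive mortality rate that may be incomplete or biased, rather than a wrong development decision. The correction is cheap enough to be worth making.

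**What to change.** 1. Retrieve Day-30 vital status from records, where consent permits, for every randomised patient, treated or not. With recruitment closed, this matters more than rewording Protocol 5.7.
2. Reconcile Protocol 5.2.3, 5.7 and 7.4.2 on what is collected for untreated patients, and state in the report which rule sites followed.
3. In SAP Table 3 add a row for Day-30 all-cause mortality in all randomised patients by assigned arm, next to the FAS row. Show any unknown status as unknown.
4. Report never-treated patients by arm with reason and timing, and state how a control patient given no antiviral was classified for the FAS.

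The cost is one records check per untreated patient and one extra table row. The count by arm can build on the disposition display already planned in SAP 11.1.

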5.8 EVALUATIONS DURING FOLLOW-UP

	ASSESSMENT/PROCEDURES	TIME
Clinical evaluation	
 COVID-19-related signs and symptoms checklist (Appendix 10 – COVID-19 signs/symptoms checklist). 	Daily while admitted, upon discharge, Day 8 ± 1 Day 15 ± 1 Day 30 ± 2 Day 45 [¥] ± 2 and if readmission.

ASSESSMENT/PROCEDURES	TIME

 Clinical status (11-point WHO Clinical Progression Scale) Vital signs will include body temperature (°C), SBP (mmHg), DBP (mmHg), pulse rate (bpm) and respiratory rate (breaths/min). Targeted physical examination. A targeted physical examination will include heart, lungs, abdomen, extremities plus CNS assessment, based on the investigator's decision as per clinical evolution. Lung function tests include PaO₂, FiO₂ and SpO₂. PaO₂/FiO₂ ratio will also be measured; either Ellis or Rice formulae can be used to estimate PaO₂/FiO₂ ratio (Appendix 5 - Imputation of PaO₂/FiO₂ ratio). 	*Only assessment of COVID-19-related signs and symptoms checklist

 Concomitant therapies. Subsequent medications for SARS CoV 2 infection. Subsequent medications for the underlying disease. 	Throughout follow-up period, if changes
Laboratory tests*	Haematology: haematocrit, RBC, differential WBC counts

	ASSESSMENT/PROCEDURES	TIME
	(including neutrophil and lymphocyte counts), platelet count and haemoglobin (See Appendix 8 – Clinical Laboratory Analyses).	Day 15 ± 1 Day 30 ± 2 If clinically indicated (AE), and if readmission
	Biochemistry: Liver function test [ALT, AP, AST [†] , albumin, total bilirubin (direct bilirubin if total is abnormally elevated)], LDH, glucose [fasting], sodium, potassium, calcium, BUN/urea, GGT, creatinine, calculated creatine clearance [CKD-EPI], CPK, amylase, lipase, procalcitonin, ferritin, and CRP (See Appendix 8 – Clinical Laboratory Analyses).	
	Coagulation: D-Dimer (See Appendix 8 – Clinical Laboratory Analyses).	
	Urine analysis (semi-quantitative elemental tests for specific gravity, blood, pH, proteins, bilirubin, glucose, ketones, nitrites, and qualitative analysis of the sediment).	Repeat whenever clinically indicated for AE evaluation.
Inflammatory and immunological biomarkers in blood (central laboratory)	Luminex® Multiplex cytokine assessment.	Day 8 ± 1 Day 15 ± 1 Day 30 ± 2
Anti-SARS-CoV-2 (central laboratory)	IgG/M anti-protein S and N.	Day 30 ± 2
	T-cell response (IFN- γ) to SARS-CoV-2 S-protein (Quantiferon®).	

	ASSESSMENT/PROCEDURES	TIME
Detection of SARS-CoV-2	qRT-PCR in oro/naso-pharyngeal exudates (central laboratory).	Day 8 ± 1 Day 15 ± 1 Day 30 ± 2 Day 45 ± 2
	Rapid Antigen Test (at site).	Every other day while admitted, Day 8 ± 1 Day 15 ± 1 Day 30 ± 2 Day 45 ± 2
ECG**	Cardiac rhythm will be identified in ECG intervals of at least 30 seconds of duration, PR interval, QT interval (raw), heart rate and QRS complex, with specialist assessment/judgment of further evaluation if appropriate.	Whenever clinically indicated for AE evaluation.
Chest X-ray	Qualitative evaluation and Brixia score (See Appendix 9 – Brixia Score). (Submission to central review)	Day 15 ± 1 Day 30 ± 2
Pharmacokinetics (central laboratory)	(See details in Section 7.6).	Day 8 (±1) (see details in Section 7.6).
Survival status		Throughout the treatment period
Hospitalisation status		Throughout the treatment period
Adverse events	As per NCI-CTCAE v.5***	Throughout the treatment period.

* Central laboratory for all the tests

** Triplicate.

*** The “AE form” will be used to report signs and symptoms and medical history in case of any significant change (improvement or worsening) during the study, as well as for events that occur after the first drug infusion or any event related to a study procedure within the study period (according to ICH guidelines).

¹See [Section 7.2.1 Adverse Events of Special Interest \(AESIs\)](#).

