EFFICACY EVALUATION CRITERIA	
Efficacy parameters include:
 
 • Mortality (all-cause and related to COVID-19); • COVID-19 signs and symptoms will be collected daily from Day 1 until the end of hospital care; thereafter at Days 4, 8 (±1), 15 (±1), 30 (±2), 45 (±2), and 60 (±3); • Clinical status is assessed using the WHO 11-point Clinical Progression Scale; • Lung function tests include fraction of inspired oxygen (FiO₂) (%), oxygen saturation (SpO₂), partial pressure of oxygen (PaO₂) (mmHg) [could be imputed from oxygen saturation (SpO₂)]. PaO₂/FiO₂ ratio will also be calculated (See Appendix 5 - Imputation of PaO₂/FiO₂ ratio); • SARS-CoV-2 quantitative real-time-reverse transcription polymerase chain reaction test (qRT-PCR) will be performed by central laboratory from oro-nasopharyngeal exudates on Day 1 before administration of the study drug and repeated at Days 4 (±1), 8 (±1), 15 (±1), 30 (±2), 45 (±2), and 60 (±3). Name of the variant will be collected if known; • SARS-CoV-2 Rapid Antigen test (RAT) will be performed every other day from Day 4 until discharge, and always at Days 1, 4 (±1), 8 (±1), 15 (±1), 30 (±2), 45 (±2), and 60 (±3); if RAT is positive at discharge, RAT should also be monitored on a weekly basis until negative. A

	
negative result should be confirmed with a second RAT within 48 h, by the investigator team;
 
 • Humoral response anti-SARS-CoV-2; • T-cell response against SARS-CoV-2; • Additional therapies for COVID-19; • Type and dates of oxygen support; • Radiological scores (chest X-ray, Brixia score; centrally assessed) (See Appendix 9 – Brixia Score); • Death date and reason; • Dates of discharge from ICU or hospital, and date of eventual re-admission; • Inflammatory and immunological biomarkers, including C-reactive protein (CRP), procalcitonin, lactate dehydrogenase (LDH), ferritin, neutrophil-to-lymphocyte ratio, ALC, D-Dimer, and multiplex cytokines assay; • Compliance with scheduled therapies for the underlying disease.
PHARMACOKINETIC (PK) EVALUATIONS	
PK analysis of plitidepsin concentration-time data will be performed in 30 patients using non-linear mixed-effects modelling. Individual PK parameters will be (See Section 7.6):
 
 • Plasma total area under the curve (AUC). • Plasma total clearance (CL).

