3.1 PRIMARY ENDPOINT

- *Efficacy primary endpoint*
 - 1-month[†] all-cause mortality rate. [†](Day 30 since randomisation).

3.2 KEY SECONDARY ENDPOINT.

- Time to confirmed negativisation in SARS-CoV-2 antigen test or RT-PCR Ct > 30.

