7. STUDY EVALUATIONS

7.1 EFFICACY

7.1.1 Test for COVID-19

A SARS-CoV-2 Rapid Antigen Test, provided by the Sponsor, will also be performed at the site by the research team on Day 4 until discharge, and always at Days 1, 4 (± 1 day), 8 (± 1 day), 15 (± 1 day), 30 (± 2 days), 45 (± 2 days), and 60 (± 3 days); if RAT is positive at discharge, RAT should also be monitored on a weekly basis until negative. A negative result should be confirmed with a second RAT within 48 h, by the investigator team.

Quantitative PCR to assess viral load on Day 1 before initiation of treatment and on Days 4 (± 1 day), 8 (± 1 day), 15 (± 1 day), 30 (± 2 days), 45 (± 2 days), and 60 (± 3 days) (see [Appendix 13 - Schedule of Assessments and Procedures](#)), will be performed by a central laboratory. Based on these assessments, changes in viral load respect to Day 1 will be calculated for each patient. The proportion of patients with either $> 2 \log 10$ reductions or undetectable SARS-CoV-2 on each time point will also be assessed.

Details regarding the collection, processing, storage, and shipment of oro-nasopharyngeal samples for qPCR testing will be provided to each investigational site before initiation of the study in the form of a laboratory manual. All oro-nasopharyngeal samples for qPCR must be

processed and shipped as specified in the laboratory manual to maintain sample integrity. Any deviations from the processing steps (e.g., sample collection and processing steps, interim storage, or shipping conditions), including any actions taken, must be documented and reported to the Sponsor. On a case-by-case basis, the Sponsor may make a determination as to whether sample integrity has been compromised. Any deviation from the specified sample handling procedure that results in compromised sample integrity will be considered a protocol deviation.

Samples will be analysed using validated analytical methods, as approved by the Sponsor.

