As each basket completes, they would have been evaluated for efficacy, with information gained being used to update the analyses of successive baskets.

Due to the premature study closure no Bayesian specific outputs or sensitivity analyses will be generated

Secondary Endpoints/Other Endpoints

Frequency tables will be prepared for categorical variables, and continuous variables will be described by means of summary tables, which will include the median, mean, standard deviation, interquartile range, minimum, and maximum of each variable.

Frequentist methods will be calculated. Counts and percentages, with their corresponding exact confidence intervals, will be calculated for the binomial endpoints.

Time-to-event variables (e.g. key secondary endpoint) and their set time estimates will be defined as time from randomization to their corresponding event + 1 (see 8.3 section) and analysed according to the Kaplan-Meier method.

Key secondary endpoint, time to confirmed negativisation in SARS-CoV-2 antigen test or RT-PCR Ct > 30, will be analysed according to the Kaplan-Meier method.

<NOTE: Due to the premature study closure no complex specific outputs or sensitivity analyses will be generated>.

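### Antigen testing thins out after discharge, and protocol text and table disagree on by how much, so recorded clearance time depends modestly on length of stay

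*Protocol*

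**What the plan says.** The key secondary endpoint (Protocol 3.2, SAP 8.3) is "Time to confirmed negativisation in SARS-CoV-2 antigen test or RT-PCR Ct > 30".

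The RAT schedule appears in three places in the protocol, and they differ:

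- Synopsis, efficacy evaluation criteria: "SARS-CoV-2 Rapid Antigen test (RAT) will be performed every other day from Day 4 until discharge", plus the fixed visit days.
- Section 7.1.1: the test "will also be performed at the site by the research team on Day 4 until discharge", with no interval given, plus the fixed visit days.
- Section 5.8 table: "Every other day while admitted", plus Days 8, 15, 30 and 45. Day 60 is covered in Section 5.9.

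The synopsis and Section 7.1.1 add a rule for after discharge: "if RAT is positive at discharge, RAT should also be monitored on a weekly basis until negative". The Section 5.8 table does not carry it. Both texts also ask for a negative result to be confirmed by a second RAT within 48 hours. Central PCR is on the fixed visit days only, in or out of hospital.

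For analysis, SAP 11.6 states: "Key secondary endpoint, time to confirmed negativisation in SARS-CoV-2 antigen test or RT-PCR Ct > 30, will be analysed according to the Kaplan-Meier method". SAP 9.0 censors patients without the event at their last valid assessment. Neither document allows for unequal test spacing or limits the between-arm comparison to days on which every patient is tested.

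**The concern.** Clearance happens at an unobserved moment between two tests, and the plan dates it at the later test. The gap between tests is about 2 days in hospital. After discharge it is up to 7 days under the weekly rule, and 7 to 15 days on the table schedule once Day 8 has passed. Discharge is a post-randomisation outcome in an open-label trial, and time to sustained end of hospital care is itself an efficacy endpoint (Protocol 3.3.1). If length of stay differs by arm, so does the delay between true and recorded clearance.

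The direction is predictable: the arm that leaves hospital sooner looks slower to clear virus. SAP 6.0 says the descriptive tables will allow a numerical comparison of the arms, and SAP 11.0 plans an inverse Kaplan-Meier figure for this endpoint. A reader comparing the curves by eye would have no warning that part of any gap between visits may come from the test schedule.

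**Working it through.** The documents give no effect size or power for this endpoint, so there is no stated figure to reproduce. The check asks how far the schedule alone can separate two arms with identical true clearance.

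**1. One patient.** Recorded day = first scheduled test day on or after the true clearance day. Test days taken from the documents:

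- Inpatient throughout: every second day from Day 4, plus the fixed visits (Days 4, 8, 15, 30, 45, 60).
- Discharged Day 6, weekly rule: Days 4 and 6, then 13, 20, 27, 34 and so on, plus the fixed visits.
- Discharged Day 6, table only: Days 4 and 6, then the fixed visits.

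| True day | Inpatient | Discharged Day 6, weekly | Discharged Day 6, table |
|---|---|---|---|
| 9 | 10 | 13 | 15 |
| 16 | 16 | 20 | 30 |
| 17 | 18 | 20 | 30 |
| 31 | 32 | 34 | 45 |

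For true clearance spread evenly over Days 8 to 30, the mean delay is 1.0, 2.5 and 6.2 days, and the maximum about 2, 7 and 15 days.

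**2. Two arms, Weibull model.** Assumptions, none of them in the documents unless stated: clearance shape 1.5 with median 8, 12 or 17 days, the same in both arms; discharge shape 1.3 with median Day 6 in one arm and Day 14 in the other; stay independent of clearance; perfect tests on nominal days; a test at discharge; event dated at the first negative test. The 17-day value is the protocol's compassionate-use median (Section 1.2.1.3.3), which was measured to Ct > 36, not Ct > 30.

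| Short stay v long stay | Weekly rule | Table schedule |
|---|---|---|
| Difference in mean recorded time, across the three true medians | about 0.3–0.4 days | about 0.9–1.2 days |
| Difference in recorded clearance by Day 14 | about 5–6 points | about 7–11 points |
| Recorded medians, true median 17 | 20 v 19 or 20, depending on rounding of the discharge day | 30 v 22 |
| Recorded medians, true median 8 or 12 | within a day | within a day |

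At true median 17 on the table schedule the mean recorded times are 25.0 and 23.8 days, a difference of 25.0 − 23.8 = 1.2 days. Cumulative clearance is 44% v 44% at Day 15 and 80% v 80% at Day 30. The 30 v 22 gap arises because the curves are near 50% during the long stretch between Days 15 and 30. With median stays of 6 and 10 days, both medians are 30.

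**3. Two arms, lognormal model.** Clearance log-SD 0.6, stay log-SD 0.5, median stay 6 v 12 days. The hazard ratio (HR) is short stay v long stay; 1.00 is the truth.

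| True median | Weekly: medians, HR | Table: medians, HR |
|---|---|---|
| 10 | 13 v 12, 0.96 | 15 v 12, 0.90 |
| 17 | 20 v 20, 0.98 | 30 v 30, 0.94 |

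**4. After the fix.** When only the fixed visits are used for everyone, the HR is 1.00 in every scenario. Both arms then have a median of Day 15 (true 10) or Day 30 (true 17), so the event date is unbiased between arms but coarse.

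**The case against.** The strongest reply is that the effect is small and little depends on it. Recruitment has closed, and SAP version 3.0 drops significance tests and the Cox model for this endpoint. The go criterion rested on mortality, which testing frequency cannot affect. If plitidepsin shortens stay, the distortion runs against it. Under the weekly rule, which two of the three texts state, the arm medians differ by a day at most in these models. Appendix 13, the schedule that Section 7.1.1 and SAP 9.0 point to, is not in the text reviewed and may carry the weekly test. All of this stands, and it is why the point is minor.

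A reader might infer more, and the documents do not support these readings:

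- **An eight-day false gap in medians should be expected.** It needs the table schedule, a 17-day true median taken from a Ct > 36 endpoint, and a wide assumed difference in stay. A looser Ct threshold would normally be reached earlier.
- **Infusions or PK sampling will keep the experimental arm in hospital and flatter it.** Infusions end on Day 3, PK sampling covers 30 patients, and no section requires admission for it.
- **A patient with a negative but unconfirmed test at discharge is lost.** The 48-hour confirmation applies regardless of admission. As worded, the weekly rule leaves out only a patient whose confirmatory test is missed or turns positive.

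There is also a fair objection to making fixed visits the only analysis: it discards the every-other-day tests. The fix below therefore keeps them.

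**Conclusion.** The concern holds in a limited form. Test spacing depends on discharge, the protocol's texts disagree on the post-discharge schedule, and ordinary Kaplan-Meier carries that spacing into the recorded clearance time. Between common visits the arm discharged sooner is recorded as clearing later. At the common visits the arms agree.

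For one patient the delay can reach about 7 days under the weekly rule or 15 days on the table schedule. Between arms it is modest: about 1.2 days at most in mean recorded time, and HRs of 0.90 to 0.98 where the truth is 1.00. These figures rest on assumed lengths of stay and clearance distributions; with equal stay the artefact is zero. The documents do not show that stay will differ by arm, only that it may. Severity is minor, because the current SAP reports this endpoint descriptively.

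**What to change.** 1. Reconcile the synopsis, Section 7.1.1 and the Section 5.8 table so that they give one RAT schedule, in hospital and after discharge. Since enrolment has closed, also state in the study report which schedule sites followed.
2. In SAP 11.6 and Table 3, make the between-arm comparison for this endpoint the cumulative proportion cleared by arm at the common visits: Days 4, 8, 15, 30, 45 and 60.
3. Keep the Kaplan-Meier curve based on all RATs with a note that test spacing differs between inpatients and discharged patients, or replace it with an interval-censored (Turnbull) estimate, which uses every test and allows for unequal gaps.

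The cost is a correction to the protocol text, a few lines in the SAP and one extra table or curve from data already collected. The drawback is a coarser comparison at the fixed visits.
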